9. STUDY DRUG

Contents and Packaging

Lotilaner has been formulated as a topical ophthalmic preparation, TP-03. The vehicle of TP-03 is the same formulation without the inclusion of lotilaner. Both are supplied as a 10 mL fill in an 11-ml-low-density polyethylene ophthalmic dropper bottle. [REDACTED]

[REDACTED]

Storage and Handling

Both preparations should be stored at ambient room temperature, 20° to 25° C (68° to 77° F) per USP. Excursions between 15° and 30° C (59° and 86° F) that are experienced in pharmacies, hospitals, ophthalmic practices, warehouses, and during shipping are allowed. There are no light requirements, but extreme humidity conditions should be avoided.

Participants will be instructed to store the study drug at room temperature in a climate-controlled environment avoiding extreme heat or cold and extreme humidity conditions. In addition, participants will be advised that the study drug should not be kept at temperatures higher than 40° C (or 104° F) for longer than 24 hours.

10. STUDY PROCEDURES AND ASSESSMENTS

10.1. INFORMED CONSENT

Prior to performing any study-specific procedures, potential study participants will be provided with an IRB-approved informed consent form and be given a chance to review and ask questions before written informed consent is obtained.

The potential study participant will be asked to sign and date the informed consent form. The individual explaining the consent will also sign and date the consent form as required. The original will be retained with the potential study participant's medical records and a copy will be provided to the potential study participant.

10.1.1. RECONSENTING

Prior to performing any study-specific procedures specific to Day 115, potential study participants who exited the study per protocol version 3.0 and participants who have not exited the study will be provided with an IRB-approved informed consent form and given a chance to review and ask questions before written informed consent is obtained.

The potential study participant or enrolled study participant will be asked to sign and date the informed consent form. The individual explaining the consent will also sign and date the consent form as required. The original will be retained with the study participant's medical records and a copy will be provided to the study participant.

10.2. PARTICIPANT ID ASSIGNMENT

While undergoing screening, potential study participants who sign an informed consent form will be identified by their initials and unique subject ID. For the initials, a dash (-) will be used in place of the middle initial for potential participants who have no middle name. The unique subject ID will consist of the site number followed by a hyphen and then the screening number. For each site, the screening number is a 4-digit number assigned in sequential order beginning with 0101.

If a potential study participant has provided written informed consent and met all eligibility criteria, the participant will be considered enrolled in the study. Once the participant has been enrolled, the site will supervise the administration of the first dose of the study medication.

Potential participants who have provided written informed consent but fail to meet eligibility criteria and are screened again on a different day will be assigned a new unique subject ID that is

different from their initial unique subject ID (next sequential screening number available at the site).

Participants who enrolled and exited the study but agree to return for the Day 115 visit will retain their originally assigned unique subject ID. Rescreened participants who enrolled and exited the study will retain their second unique subject ID assigned.

10.3. STUDY TREATMENT COMPLIANCE

Participants will be instructed on proper instillation and storage of the study drug and provided with written instructions. Participants will be instructed to record in a dosing compliance diary on a daily basis. During in-office study visits, dosing compliance will be assured by a review of the dosing diary to assess adherence to the protocol regarding the administration of the study product.

10.4. VISIT SCHEDULE AND EXAMS

Participants will remain in the study for up to 175 days and will be seen at the following intervals: Day 1, Day 15, Day 29, Day 43, Day 57, Day 85 and Day 115.

The schedule of exams and procedures performed at these visits can be found in [REDACTED]. Descriptions of exams and procedures performed during these visits can be found in Appendix B.

For participants reporting for an unscheduled visit, assessments may be performed at the discretion of the investigator. At a minimum, corrected distance visual acuity and the occurrence of any adverse events should be assessed.

Participants who are exited from the study due to unanticipated adverse effects will be followed, if possible, until their medical outcome is determined. The investigator will provide written reports to the IRB as required.

10.5. STUDY EXIT

Participants will be exited at the Day 115 visit.

11. EARLY TERMINATION AND PARTICIPANT DISCONTINUATION

For each participant, the study will be considered completed when the Day 115 assessment has been performed in accordance with the study protocol.

Any participant may voluntarily discontinue the study at any time without prejudice. The investigator may elect to discontinue a participant for reasons unrelated to the study drug (e.g., failure to comply with the study protocol, missed visits, etc.) or for reasons related to the study drug (e.g., AE, unsatisfactory therapeutic response, etc.). Reason(s) for discontinuation should be recorded on the CRF.

Clinical Research Protocol

Protocol TRS-008

01-Feb-2023

Possible reasons for study discontinuation include the following:

- Lack of efficacy: the participant does not feel that the study drug has adequately relieved his/her symptoms
- AEs necessitating discontinuation from the study
- The participant is lost to follow-up
- Participant decision unrelated to lack of efficacy or AEs
- Reasons relating to COVID-19
- Investigator decision (specify)
- Other reason (specify)

If a participant chooses to discontinue his/her participation or is discontinued, the Exit Form will be completed regardless of other information available. Should a participant experience any difficulties requiring review between planned visits, or in case of early exit between planned visits, the Unscheduled Visit Form will be completed. Reason(s) for such a visit will be recorded on the CRF. Discontinued participants will not be replaced. Participants to be discontinued for AE(s) will be followed until the event is resolved, if possible, or considered medically stable by the investigator.

The data to be collected at the time of study treatment discontinuation may include the following:

- An AE assessment and performance of safety assessments including visual acuity and slit lamp biomicroscopy
- Any follow-up evaluations required per investigator determination

Temporary discontinuation of the study treatment could include the onset of such conditions as allergic conjunctivitis or signs or symptoms of eyelid allergy (e.g., injection, swelling, itching, etc.). Per investigator discretion, the study treatment could be discontinued until such a time that the adverse event has shown sufficient improvement such that the study treatment could be restarted. Re-challenging with the study treatment could help to determine if the adverse event is related to the study drug. It should be noted that discontinuation from use of the study treatment does not mean discontinuation from the study, and remaining study procedures should be completed as indicated by the study protocol.

The following actions must be taken if a participant fails to return to the clinic for a required study visit:

- The site will attempt to contact the participant and reschedule the missed visit as soon as possible, counseling the participant on the importance of continuing the administration of the study drug and of maintaining the assigned visit schedule. In addition, the site should ascertain if the participant wishes to and/or should continue in the study.
- Before a participant is deemed lost to follow-up, the investigator or designee will make every effort to regain contact with the participant (where possible, three telephone calls and, if necessary, a certified letter to the participant's last known mailing address or local equivalent methods). These contact attempts should be documented in the participant's medical record or study file.

- Should the participant continue to be unreachable, he or she will be considered to have discontinued the study with a primary reason of lost to follow-up.

The principal investigator reserves the right to discontinue the study for any safety, ethical or administrative reason at any time.

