8.5. DAY 115 (+60 DAYS)

Participants who were exited from the study after completing dosing of study drug through Day 85 and participants who have not exited the study will be invited for an additional post-treatment follow-up visit on Day 115.

Procedures to be performed include:

- Reconsent the participants who were exited per protocol version 3.0 and participants who have not exited the study
- Concomitant medications review
- CDVA
- Slit lamp biomicroscopy including assessment of lid margin erythema
- Meibomian gland secretion assessment of lower lids
- Assessment of adverse events
- Study exit

At this visit, participants will be exited from the study provided they do not have any ongoing adverse events.

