17. COMPLIANCE WITH PROTOCOL

Participation in the study will be summarized by presenting the number of participants who received at least one dose of the study treatment, the number of participants who completed the study per protocol, and the number of participants who did not complete the study by reason of early discontinuation.

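### Does defining completion by the Day 115 visit leave participants who were exited at Day 85 under version 3.0 unclassified?

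*Protocol*

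**What the plan says.** Protocol Section 11 sets one completion rule for everyone: "For each participant, the study will be considered completed when the Day 115 assessment has been performed in accordance with the study protocol". Section 10.5 matches it: "Participants will be exited at the Day 115 visit".

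Other sections recognise people who had left the study before the Day 115 visit was offered to them. Section 8.5 says that those "exited from the study after completing dosing of study drug through Day 85 and participants who have not exited the study will be invited" to the additional visit. Section 10.1.1 sets out the new consent: "potential study participants who exited the study per protocol version 3.0 and participants who have not exited the study will be provided" with a consent form. Section 10.2 treats return as a matter of agreement: "Participants who enrolled and exited the study but agree to return for the Day 115 visit will retain their originally assigned unique subject ID".

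Section 17 governs the disposition summary. It opens "Participation in the study will be summarized by presenting the number of participants who received at least one dose of the study treatment", adds the number who completed per protocol, and ends with "the number of participants who did not complete the study by reason of early discontinuation". Section 11 also separates stopping drug from leaving the study, noting that "discontinuation from use of the study treatment does not mean discontinuation from the study".

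Section 12.9 plans two locks. The first covers visits through Day 85 and supports the final report. The second adds Day 115 and supports an addendum. The study visits in the SAP's protocol summary end at Day 85. SAP 2.2.6 (Subject Disposition) appears in the contents list, but its text is not in the copy reviewed. That is not a fault of the plan.

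**The concern.** Take a participant who dosed through Day 85, was exited as version 3.0 provided, and declines the later invitation. Section 11 makes no exception, so this person has not completed. Nor did the person discontinue early in any ordinary sense. If Section 17's last count means only people who stopped early, the person falls in neither outcome count, and the two counts add to less than the number dosed. If the person is placed among early discontinuations, someone who took the whole planned course is shown as a dropout.

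This could matter because the trial is a pilot meant to inform later studies (Protocol 12.1), and the share finishing the 85-day course is a figure a planner would use.

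A related point concerns adverse events. SAP 2.2.9.1 gives treatment-emergent events a start date and no end date. Applied to Day 115 data, it would pool events arising off drug with those arising on drug. Follow-up would also be longer for those who returned, because Protocol 16.4 stops recording non-serious events 7 days after the last day of participation.

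**Working it through.** The plan states no completion figure, so there is nothing to reproduce. The check sets the sections side by side and sizes the possible effect.

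**1. Who is affected.** Only people exited under version 3.0 after dosing through Day 85 who do not return. A participant still in the study who misses Day 115 is an ordinary non-completer with a recorded reason.

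**2. Do the counts add up?** Let N be the number dosed and x the number in step 1.

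- Narrow reading of Section 17 (only early stoppers are counted): completers + early discontinuations = N − x. With N = 40 and x assumed, x = 0 gives 40, x = 5 gives 35 and x = 10 gives 30.
- Ordinary reading (all non-completers, tabulated by reason): completers + non-completers = N for any x. Section 11 offers its reasons as possible ones, including participant decision and a free-text other category, so every non-completer can be given a reason.

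The shortfall therefore depends on the narrow reading, which the wording permits but does not require.

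**3. Size per person.** Inputs: up to 40 participants, randomized 1:1 (Protocol Summary), so 20 per regimen at full enrolment.

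- Overall: 1/40 = 2.5 percentage points.
- Within a regimen: 1/20 = 5 percentage points.
- With assumed counts of 1, 4 and 12: 1/40 = 2.5, 4/40 = 10 and 12/40 = 30 points. The last is an extreme. The documents give no count, and zero is possible.

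**4. Which report is affected.** Under Section 12.9 the first lock takes place once every participant has completed the Day 85 assessment or been exited, and it holds visits through Day 85. A disposition table from that lock rests on Day 85 status, since Day 115 data belong to the second lock. The Section 11 label therefore matters in the addendum. Even there, Day 85 attendance remains in the visit data, so treatment-period completion can be shown next to Day 115 attendance.

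**5. The adverse event point.** Inputs: Day 85 window −13/+7 days, Day 115 window +60 days (Protocol 8.4, 8.5), and the 7-day tail (Protocol 16.4).

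- Day 85 visit: 85 − 13 = 72 to 85 + 7 = 92. Day 115 visit: 115 to 115 + 60 = 175.
- Interval between the visits: nominally 115 − 85 = 30 days; 175 − 85 = 90 if Day 115 is as late as allowed; across both windows, 115 − 92 = 23 to 175 − 72 = 103 days.
- Off-drug share of non-serious event follow-up: exit at Day 85, 7/(85 + 7) = 7/92 = 8%; return on Day 115, (30 + 7)/(115 + 7) = 37/122 = 30%; return on Day 175, (90 + 7)/(175 + 7) = 97/182 = 53%.

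These are shares of follow-up time, not changes in an event rate. Protocol 16.4 collects onset dates, so events can be split at the Day 85 visit whenever wanted, and the first lock already keeps the main report to visits through Day 85.

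**The case for a change.** The best argument for a change is that Section 11 applies to each participant without exception. The free-text reason would solve the arithmetic only by listing a person who finished the planned course as discontinued. The lost-to-follow-up steps do not fit either: they apply to required visits and include advice to keep using the drug, whereas this visit is by invitation and drug is collected at Day 85. Reading completion per protocol in Section 17 as meaning the version then in force is possible, but Section 11 does not say so. A sentence of clarification would be short.

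Most of this stands as a description of the text. The literal rule and the version 3.0 exits do not sit neatly together, and no visible section says how a non-returner is labelled. What does not stand is the consequence. The first lock keeps the main report at Day 85, the group may be empty, and SAP 2.2.6 may already settle the label. Nor is the change quite as cheap as a sentence suggests: rewording Protocol 10.5, 11 and 17 is an amendment, and Section 19 requires IRB approval before it takes effect. That buys only a label that the study team can settle from data already held.

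On adverse events, it is fair that the visible definition has no end date. But safety is descriptive only, both regimens receive the same invitation, and drug-related events are counted separately, so the treatment-related endpoint is largely unaffected.

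**Conclusion.** No change to the plan follows. This is a gap in labelling that analysts would fill sensibly: report who attended Day 85, report separately who attended Day 115, and describe a non-returner from the version 3.0 group as such. The possible effect is 2.5 points of completion per person overall, or 5 within a regimen, for an unknown number of people, and it falls mainly in the addendum. No data are lost, and no efficacy test, alpha level, sample size or between-regimen comparison changes.

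The conclusion assumes that Day 85 attendance and event onset dates are recorded as the protocol requires, that the first report uses the Day 85 lock as Section 12.9 describes, and that SAP 2.2.6 does not direct that these people be counted as early discontinuations. If it did, the main disposition table would understate treatment completion, and the point would deserve another look.

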12. STATISTICAL CONSIDERATIONS AND ANALYSIS

12.1. SAMPLE SIZE

There is no prior data available for TP-03 in the treatment of MGD to use as a performance estimate. The sample size of 40 participants was selected based on clinical and practical considerations. Results from this study will be used to inform the design of subsequent studies to demonstrate a therapeutic effect.

12.2. RANDOMIZATION

This is a randomized, double-masked study. A blocked randomization schedule will be prepared and used to package the afternoon dose of the drug (all participants receive TP-03 for the morning and evening doses). The drug will be dispensed at the site sequentially from the available inventory. The bottle number dispensed will be recorded.

12.3. GENERAL CONSIDERATIONS

The sample size, mean and standard deviation will be presented for continuous analysis variables or, if appropriate, the sample size, median and range. Categorical variables will be presented as the count and percentage for each category. Statistical tests will be two-sided and evaluated at an α of 0.05 unless otherwise specified. No adjustment will be made for multiplicity.

12.4. MISSING DATA

Missing data will not be imputed.

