**Randomized, Double-Masked, Pilot Study Comparing the Safety and Efficacy
of Two Dosing Regimens of TP-03 for the Treatment of Meibomian Gland
Dysfunction in Patients with *Demodex* Lid Infestation (Ersa)**

Protocol Number: TRS-008

[REDACTED]

[REDACTED]

[REDACTED]

[REDACTED]

IND Sponsor: Tarsus Pharmaceuticals, Inc.

NCT05454956

PROTOCOL SUMMARY

TITLE	Randomized, Double-Masked, Pilot Study Comparing the Safety and Efficacy of Two Dosing Regimens of TP-03 for the Treatment of Meibomian Gland Dysfunction in Patients with Demodex Lid Infestation (Ersa)
TEST ARTICLE	TP-03, lotilaner ophthalmic solution, 0.25%
OTHER TEST ARTICLE	Vehicle of TP-03 to maintain masking of BID dosing
OBJECTIVE	
To evaluate the safety and efficacy of TP-03, 0.25%, BID versus TID dosing for the treatment of meibomian gland dysfunction in patients with Demodex lid infestation.
 
Efficacy will be evaluated by the assessment of lower lid meibomian gland secretion, erythema of the lid margins, [REDACTED], [REDACTED].
 
Safety will be determined by assessing adverse effects related to treatment [REDACTED]
 
[REDACTED]

CLINICAL HYPOTHESIS	Treatment with TP-03, 0.25%, TID will result in a greater improvement from baseline than BID treatment for 85 days in the signs [REDACTED] of MGD with no significant increase in ocular irritation.
STUDY DESIGN	Prospective, randomized, two-arm, double-masked, parallel treatment study
NUMBER OF PARTICIPANTS	Up to 40
PARTICIPANT POPULATION	Participants with evidence of meibomian gland dysfunction in the presence of Demodex infestation
DESCRIPTION OF SITES	Up to six sites in the United States
STUDY DURATION	Approximately 9 months
RANDOMIZATION	1:1
STUDY VISITS	Study visits will take place at Day 1, Day 15, Day 29, Day 43, Day 57, Day 85 and Day 115
SAFETY MEASURES	
 • Adverse events • [REDACTED] • Slit lamp biomicroscopy findings
EFFICACY MEASURES	
 • Lower lid meibomian gland secretion assessment 
 ○ Total meibomian gland score

Clinical Research Protocol

Protocol TRS-008

[figure not shown]
01-Feb-2023

	
• Lid margin erythema

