12.7. STATISTICAL ANALYSES

Efficacy Analyses

Efficacy analyses comparing the outcome between dosing regimens will be performed on the change from baseline, except for the post treatment survey, using either the Student's *t*-test or Wilcoxon rank-sum test as appropriate.

Efficacy analyses examining the change from baseline for both dosing regimens combined will use either a paired *t*-test or a Wilcoxon signed-rank test as appropriate. A one-sided test for an improvement from baseline will be evaluated using an α of 0.025.

Safety Analyses

Clinically meaningful changes from baseline (Day 1) in visual acuity and slit lamp biomicroscopy will be summarized for each follow-up visit. A clinically meaningful change for visual acuity will be a change of more than 2 lines on the ETDRS chart (change greater than 0.2 logMAR). A clinically meaningful change in slit lamp biomicroscopy will be a change of 2 or more grades.

Adverse event data will be summarized by the MedDRA preferred term and listed.

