Efficacy Measures	
 • Lower lid meibomian gland secretion assessment 
 ○ Total meibomian gland score ■ [REDACTED] ■ [REDACTED] • Lid margin erythema 
 ■ [REDACTED]
Statistical Considerations	
This is a pilot study to compare the safety and efficacy of two different dosing regimens, BID and TID, of TP-03 for the treatment of MGD. There are no prior data available to perform a sample size estimate. The sample size of 40 participants was selected based on clinical and practical considerations.

Statistical Analysis Plan	
Safety measures will be summarized for each treatment regimen and both treatment regimens combined using descriptive statistics.
 
Efficacy measures will be compared between dosing regimens as the change from baseline using either the t-test or Wilcoxon rank-sum test as appropriate. Comparisons will be two-sided using an α of 0.05. No adjustment will be made for multiple comparisons. Additional analyses will be performed examining the change from baseline in the efficacy measures for both treatment regimens combined.

2 Statistical Methodology

[figure not shown]
[figure not shown]
[figure not shown]
[figure not shown]
[figure not shown]
[figure not shown]
[figure not shown]
[figure not shown]

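### On the visible text, a Day 85 MGSS comparison drops anyone without a Day 85 value and leaves their Day 15–57 scores unused, so response-related loss that differs between arms can bias BID versus TID

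*Protocol*

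**What the plan says.** Protocol section 12.4 is a single sentence: "Missing data will not be imputed". Section 12.7 states that "Efficacy analyses comparing the outcome between dosing regimens will be performed on the change from baseline", with Student's t-test or the Wilcoxon rank-sum test as the tool. The SAP's protocol summary agrees: "Efficacy measures will be compared between dosing regimens as the change from baseline using either the t-test or Wilcoxon rank-sum test as appropriate".

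MGSS is assessed at Day 1 and at Days 15, 29, 43, 57 and 85 (Protocol sections 8.1–8.4). The clinical hypothesis in the Protocol Summary is that TID dosing "will result in a greater improvement from baseline than BID treatment for 85 days in the signs" of MGD. No visible text names Day 85 as the primary efficacy visit. It is inferred from this hypothesis and from section 12.9, which locks and unmasks the data after Day 85 for the main report.

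On leaving the study, Protocol section 11 lists among the reasons "Lack of efficacy: the participant does not feel that the study drug has adequately relieved his/her symptoms" and "AEs necessitating discontinuation from the study", and adds "Discontinued participants will not be replaced". Several rules limit the losses. Stopping study treatment "does not mean discontinuation from the study, and remaining study procedures should be completed as indicated by the study protocol", missed visits are rescheduled, and under section 15 a medical need for prohibited treatment does not end participation.

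**The concern.** A two-sample test on Day 85 change needs a Day 85 value. With no imputation, a participant who leaves after Day 57 contributes nothing to that test, despite four post-baseline scores on file. Those scores can still enter tests at their own visits.

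The omission is harmless if loss is unrelated to response, or if the same kinds of participant leave both arms at the same rate. The arms differ in active dose frequency, however, and both lack of efficacy and adverse events are recognised reasons to leave. Poor responders could leave one arm more often, or the arms could lose different kinds of participant in equal numbers. Equal dropout counts therefore do not settle the matter. Protocol section 12.1 says the results will inform the design of later studies, so the estimated regimen difference matters as well as the p-value.

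**Working it through.** **Inputs from the documents.** Up to 40 participants randomised 1:1, so 20 per arm; two-sided α of 0.05; MGSS range 0–45; post-baseline visits at Days 15, 29, 43, 57 and 85. The plan gives no SD, effect size, power or dropout figure, so it has no figure to reproduce.

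**Assumptions.** No true difference; normal data; correlation between visits ρ of 0.5 or 0.7; Day 1 MGSS correlated −0.5 with change; a latent exit score correlated r = 0.7 with the change that drives exit (0.35 as a weaker case). All biases are in SDs of the Day 85 change.

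**Step 1: bias by hand.** If the k lowest of 20 exit scores leave, the mean exit score of those who stay rises by

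b(k) = −(sum of the k smallest expected normal order statistics for n = 20) / (20 − k).

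The six smallest expected values are −1.867, −1.408, −1.131, −0.921, −0.745 and −0.590. Hence b(1) = 1.867/19 = 0.098; b(2) = 3.275/18 = 0.182; b(3) = 4.406/17 = 0.259; b(4) = 5.327/16 = 0.333; b(6) = 6.662/14 = 0.476.

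The bias in the Day 85 difference is r × Δb if exit follows the Day 85 change, and r × ρ × Δb if it follows the Day 29 change.

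| Loss (of 20 per arm) | Δb | Exit follows Day 85: 0.7Δb | Exit follows Day 29: 0.35Δb to 0.49Δb |
|---|---|---|---|
| 1 vs 4, poor responders | 0.333 − 0.098 = 0.235 | 0.16 | 0.08–0.12 |
| 2 vs 6, poor responders | 0.476 − 0.182 = 0.294 | 0.21 | 0.10–0.14 |
| 3 vs 3, poor vs random | 0.259 | 0.18 | 0.09–0.13 |
| 3 vs 3, poor vs good | 2 × 0.259 = 0.518 | 0.36 | 0.18–0.25 |
| 3 vs 3, same mechanism | 0 | 0 | 0 |

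**Step 2: simulation, 4,000 trials per setting.** The t-test on available Day 85 change was compared with a REML repeated-measures model (unstructured covariance, regimen-by-visit means, Day 1 MGSS, Kenward-Roger degrees of freedom). Leavers were last seen at Day 29, 43 or 57. Each cell gives bias and type I error.

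| Setting | Exit follows | t-test | Model |
|---|---|---|---|
| 1 vs 4 and 2 vs 6, poor | Day 29 | 0.08–0.15 SD; 5.6–8.7% | within 0.007 SD; 4.8–5.6% |
| same | Day 85 (unseen) | 0.15–0.21 SD; 7.8–10.5% | 0.05–0.13 SD; 6.2–7.8% |
| 3 vs 3, poor vs random | Day 29 | 0.10–0.12 SD; 6.1–7.0% | within 0.008 SD; 5.1% |
| same | Day 85 (unseen) | 0.18 SD; 9.3–9.4% | 0.07–0.11 SD; 5.9–7.1% |
| 3 vs 3, poor vs good | Day 29 | 0.18–0.26 SD; 8.3–13.0% | within 0.003 SD; 5.2–5.6% |
| same | Day 85 (unseen) | 0.36 SD; 21.0–21.4% | 0.15–0.22 SD; 9.3–13.0% |

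With 3 vs 3 under the same mechanism, or 2 vs 6 at random, bias was within 0.006 SD for both methods. At r = 0.35 the t-test bias fell to 0.04–0.19 SD (type I error 4.9–8.3%); the model was within 0.009 SD (4.4–5.4%), or 0.03–0.11 SD (4.9–6.9%) for unseen-driven exit. Monte Carlo error is about 0.005 SD for bias and 0.35 points for a 5% error rate. The t-test biases agree with Step 1.

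**Step 3: a second set of assumptions.** A large-sample check assumed an SD of 6 MGSS points, visit correlation declining with distance (0.8 between adjacent visits), and dropout depending on the last observed change. The TID − BID improvement was biased by −0.87 points (0.15 SD) with 25% vs 5% loss of poor responders, the heavier loss on BID. At 15% loss in each arm the bias was −0.68 points (0.11 SD) if poor responders left BID and random participants left TID, and −1.39 points (0.23 SD) if poor responders left BID and good responders left TID. It was about zero when the mechanism and rate were the same, or loss was unrelated to response. A likelihood estimate using all visits was within 0.02 points of zero in every case.

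**Step 4: scale.** With complete data the standard error is √(2/20) = 0.316 SD. The difference detectable with 80% power is (1.960 + 0.842) × 0.316 = 0.886 SD, or 2.802 × √(2/17) = 0.961 SD with 17 per arm.

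**The case against.** The strongest objection is that the relevant SAP text cannot be read. Section 2.2.7 on missing data and most of section 2.2.8 on efficacy are absent from the supplied copy, as are 2.2.4 (study populations) and 2.2.6 (disposition). They may already contain a model or a listing. That stands: the finding covers the visible text only.

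The size can also be challenged. No dropout rate is given. The 21% error rate needs poor responders to leave one arm and good responders the other, with exit following a value nobody saw. The lack-of-efficacy reason concerns felt symptoms, whereas MGSS is an examiner-graded sign, so a correlation of 0.7 may be too high. Both arms instil three drops a day and receive active drug morning and evening, which makes sharply different exit patterns less likely. The Day 85 window of −13/+7 days will also rescue some values. All of this lowers the expected bias without removing it; the weaker-link results show the reduced size.

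The bias is mostly below one standard error, in an exploratory study with no power calculation. That is true, and it keeps the point from being critical.

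Finally, the model is an imperfect remedy. When exit follows the unseen Day 85 value, 35–62% of the bias remains, or 65–67% if Day 1 MGSS is unrelated to change. Its smaller standard error (0.27–0.30 against 0.31–0.35 SD) comes from adjusting for Day 1 MGSS and disappears if that score is uninformative. The simulations used normal data and the t-test, so they do not give error rates for the rank-sum option on a bounded score.

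**Conclusion.** The concern holds on the visible text. A Day 85 comparison would exclude participants without a Day 85 MGSS and make no use of their earlier scores. The regimen difference can be biased when loss is related to response and differs between arms in rate or in mechanism.

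With an exit correlation of 0.7, the plausible size is 0.08–0.26 SD if exit follows observed values and 0.15–0.36 SD if it follows unseen ones; at a correlation of 0.35 the range is 0.04–0.19 SD. These figures rest on assumed loss rates, mechanisms and correlations, and Day 85 as the key visit is an inference. The gain is modest against the standard error, but the data are already scheduled, so the change should be made. Confidence is medium, mainly because of the unseen SAP sections.

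**What to change.** In Protocol section 12.7, for MGSS, take the Day 85 contrast from a REML repeated-measures model of change from baseline at Days 15, 29, 43, 57 and 85. Include regimen, visit, regimen-by-visit and Day 1 MGSS. Use an unstructured covariance, a named simpler structure if it does not converge, and Kenward-Roger degrees of freedom. Keep the t-test or rank-sum test on available values as a supporting analysis. Section 12.4 can stay as it is, because the model imputes nothing.

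Section 17 already counts non-completers by reason. Add a listing by regimen of participants without a Day 85 MGSS, with the reason and last observed change, and compare both numbers and reasons between arms. If the SAP already has this model, section 12.7 need only refer to it.

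The cost is one paragraph, one model and one listing, with no new visits or data. The model assumes that data are missing at random and roughly normal, and it estimates 15 covariance parameters (5 × 6 / 2) from 40 participants. It converged in every simulated trial; with complete data its type I error was 4.5–5.4%. It is a baseline-adjusted comparison, so it will not reproduce the t-test even with complete data.
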